5.5 Secondary Endpoints

Secondary endpoints will include the following:

- The change from baseline to STX209 administration in left and right superior temporal gyrus GABA levels.
- Safety and tolerability of STX209 based on Adverse Events. Measurements and evaluations

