2.1 Primary Objective (or Aim)

1. To determine whether STX209 produces a significant change in MEG target parameters compared to baseline as well as compared to placebo treatment. Secondly, to determine if the magnitude of such change is influenced by STX209 dose: 0mg (placebo) versus 15mg versus 30mg.
2. To determine whether STX209 leads to a significant change in MRS-obtained auditory cortex GABA levels compared with placebo treatment. Secondly, to determine whether the magnitude of the GABA change is influenced by STX209 dose level.
3. To determine if dose-dependent changes in MEG target parameters are correlated to dose-dependent changes in MRS target parameters in auditory cortex.

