4.3 MEG and MRI/MRS Assessment Phase: Visit 1-3

On the next three visits (scheduled to occur within 3 months of the physical examination and within 12 months of clinical/behavioral testing) MEG, MRI and MRS measures will be collected at each study visit. Upon arrival, vital signs will be collected. Then pre-drug MEG data will be collected to obtain baseline measures. At the conclusion of the baseline MEG scan, participants will be randomly administered a single-dose of Placebo and single-dose of STX209 in order of smallest to largest dose (15mg, 30mg) (see Section 3.2). Based on advice from Clinical Research Associates, LLC (CRA), given the time course of plasma STX209 levels, the MEG examination will be repeated 60 minutes after drug administration. Following the MEG exam, subjects will obtain a 3T MRI to obtain an anatomic 3D image (MP-RAGE) and bilateral STG GABA and glutamate measures (MEGAPRESS MRS). At the end of the scanning visit AE will be assessed via the SMURF form. Subjects will return for their imaging visit no less than four days or more than 14 days to repeat the MEG, MRI and MRS exams, each time with a different drug/placebo dose.

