Screen for Eligibility Criteria	10 min
Pre-Intake Questionnaire (Demographics)	20 min
Subtotal:	75 min
Screening Visit:	
Medical, Diagnostic, and Neuropsychological Assessments	
Procedures administered to Parent/Legal Guardian (at the same time as child testing)	
Intervention History Form	15 min
Medical History Form	30 min
Child Behavior Checklist (CBCL) (if applicable)	20 min
Social Communication Questionnaire (SCQ) (if applicable)	5 min
Social Responsive Scale-II (SRS-II) (if applicable)	10 min
Vineland Adaptive Behavior Scale (if applicable)	20 min
Autism Diagnostic Observational Scale (ADOS-2) (if applicable)	60 min
Subtotal:	2 hours and 40 min
Procedures individually administered to children:	
Physical Examination	15 min
Blood Draw	10 min
Vital Signs	10 min
Clinical Evaluation of Language Fundamentals (CELF –IV)	
(if applicable)	60 min
Wechsler Abbreviated Scale of Intelligence (WASI-II) (if applicable)	60 min
Baseline SMURF	20 min
MRI Mock Scan (optional)	30 min
Subtotal:	3 hours and 25 min

* Diagnostic and neuropsychological testing will not occur if testing scores are available (less than 12 months prior to screening visit) for re-recruited participants (data from tests will only be used if subjects who previously participated in one of our research studies, agreed to share their data on future studies). Only the medical assessments (e.g., vital signs, physical exam, medical history, intervention history form, and blood draw) will be completed for re-recruited participants at screening visit. Therefore, the screening visit will last approximately 80 minutes for re-recruited participants.

MEG Assessment 1: Visit 1

Procedures individually administered to participants at Visit 1	
Autism Diagnostic Interview – Revised (ADI-R) (if applicable)	180min
Vital Signs	10 min

Pre Drug MEG Scan	45 min
MRI Scan	30 min
Administration of STX209/Placebo	< 10 min
MRI Scan continued	30 min
Break	30-60 min
Post Drug MEG Scan	45 min
Adverse Event Assessment (SMURF)	20 min
Subtotal:	4 hours and 50 min

MEG Assessment 2: Visit2

Procedures individually administered to participants at Visit 2	
Vital Signs	10 min
Pre Drug MEG Scan	45 min
MRI Scan	30 min
Administration of STX209/Placebo	< 10 min
MRI Scan continued	30 min
Break	30-60 min
Post Drug MEG Scan	45 min
Adverse Event Assessment (SMURF)	20 min
Subtotal:	4 hours and 10 min

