5.6 Statistical Methods

Primary statistical analyses assess baseline versus post acute-dose (placebo, STX209 15 and 30 mg) changes for (1) M100 auditory latency, and (2) post-stimulus auditory gamma-band activity. For each dependent measure, ANOVAs with dose as a repeated measure will examine baseline versus post acute-dose changes (analyses showing no significant differences across time in baseline M100 and gamma measures will allow use of a single averaged baseline measure). Contrasts of *a priori* interest assess (1) a baseline versus post-acute dose change in the dependent measures averaging across STX209 15 and 30 mg, as well as (2) a change in dependent measures from baseline versus STX209 15 mg versus STX209 30 mg, with this test demonstrating an effect of dose. Secondary and exploratory analyses examine baseline to post acute-dose response changes in MRS auditory GABA concentration as well as associations between MEG functional measures and MRS GABA concentration.

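### The GABA endpoint is a change from baseline, but no section specifies a pre-dose MRS, and the sections disagree on when MRI is run relative to dosing

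*Combined protocol and SAP*

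**What the plan says.** **Endpoint and analysis.** Section 5.5 lists as a secondary endpoint "The change from baseline to STX209 administration in left and right superior temporal gyrus GABA levels". Section 5.6 says that secondary and exploratory analyses will "examine baseline to post acute-dose response changes in MRS auditory GABA concentration", and the synopsis plan says the same.

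**Objective.** Section 2.1 words the GABA objective differently: "To determine whether STX209 leads to a significant change in MRS-obtained auditory cortex GABA levels compared with placebo treatment". It names placebo only. The MEG objective beside it names both baseline and placebo.

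**Visit procedures.** Section 4.3 describes the pre-dose step as MEG alone: "Then pre-drug MEG data will be collected to obtain baseline measures". Dosing follows, then a repeat MEG at 60 minutes, and then: "Following the MEG exam, subjects will obtain a 3T MRI to obtain an anatomic 3D image (MP-RAGE) and bilateral STG GABA and glutamate measures". Section 3.1.3 puts about one hour of MRI after the post-dose MEG, and the synopsis puts MRI and MRS directly after MEG. In Table 1 the MEG row is marked as pre/post drug; the MRI row is not.

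**Timing tables.** For all three visits, Section 5.2.1 lists pre-drug MEG (45 min), MRI (30 min), dosing (under 10 min), "MRI Scan continued" (30 min), a break (30–60 min) and post-drug MEG (45 min). No MRI follows the post-drug MEG, and neither MRI block is said to contain the MRS.

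**The concern.** A change from baseline needs a pre-dose value, and the visit procedures do not collect one for GABA. The analyst would therefore have to choose the GABA contrast once the data exist. GABA is a secondary endpoint in 5.5, but it stands under the primary objectives in the abstract and in Section 2.1, so its definition should not be left open.

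The timing conflict is a separate fault. Two written flows put the MRI on different sides of the post-dose MEG. A within-subject dose comparison is cleanest when every scan is taken at the same time after dosing, and the documents do not fix that time.

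**Working it through.** **1. Can baseline mean something other than a pre-dose MRS?**
- Placebo visit: no. Section 5.6 counts placebo among the post-dose conditions, alongside 15 mg and 30 mg. Section 5.4 uses the same change-from-baseline phrasing for MEG, where baseline is the pre-drug recording.
- Screening scan: no. Neither Table 1 nor Section 4.2 lists an MRS at screening; 5.2.1 lists only an optional mock scan.

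**2. GABA values needed and supplied, per subject**
- Needed by 5.5: 3 visits × 2 times (pre, post) × 2 hemispheres = 12.
- Supplied by the synopsis, 3.1.3 and 4.3: 3 × 1 × 2 = 6, all post-dose.
- Within-visit GABA changes that can be formed: none.
- Needed for Objective 2 (each dose against placebo, both hemispheres): the same 6. All are supplied.

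**3. Reproducing the timing table.** The only stated figure that bears on this point is the Visit 2 total in 5.2.1, 4 h 10 min = 250 min.
- With a 60-min break: 10 + 45 + 30 + 10 + 30 + 60 + 45 + 20 = 250 min. This matches.
- With a 30-min break: 220 min. This does not match.
- With the 60-min break, Visit 3 adds a 15-min examination: 265 min against a stated 280. Visit 1 gives 250 min without the ADI-R or 430 min with it, against a stated 290.

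The subtotals are therefore not dependable. What follows uses only the order of the rows and their durations.

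**4. Time after dosing under each flow**

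| Event | Synopsis, 3.1.3, 4.3 | 5.2.1 tables |
|---|---|---|
| MRI before dosing | none | 30 min |
| Repeat MEG starts | 60 min | 30 + (30 to 60) = 60–90 min |
| MRI after dosing starts | 60 + (30 to 45) = 90–105 min | about 0 min |
| MRI after dosing ends | 150–165 min | about 30 min |

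The 30–45 min for MEG comes from 5.1.6 (about 30 min of recording) and 5.2.1 (a 45-min slot). The one-hour MRI comes from 3.1.3. Counting the administration step in full adds up to 10 min to the 5.2.1 column.

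The gap between the post-dose MRI windows is 90 − 30 = 60 min at the least, or 90 − 40 = 50 min with the administration step counted. They do not overlap in either case.

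**5. Could the pre-dose slot in 5.2.1 hold a baseline MRS?** Section 5.1.6 gives MEGAPRESS about 20 min and does not say whether that covers both hemispheres. If it does, 20 min fits the 30-min slot. If it is per side (an assumption), 2 × 20 = 40 min does not fit. The second block is labelled as a continuation, and 30 + 30 = 60 min equals the single one-hour MRI of 3.1.3. That reads more naturally as one examination split by dosing than as a scan repeated before and after.

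**The case against.** The strongest defence is that Section 5.2.1 does contain a pre-dose MRI slot, so a baseline MRS is conceivable. That stands as far as it goes: it is wrong to say that baseline GABA is impossible under every flow. But no section says that MRS is run in that slot, and the flow contradicts three other sections.

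A second defence is that the tables show approximate time demand rather than a protocol sequence. Their unreliable subtotals support that. However, 5.2.1 also says that it gives the timing of administration, and the row order is the same at all three visits.

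A reader might also infer more than the documents support:
- **That Objectives 2 and 3 cannot be answered.** Objective 2 is stated against placebo only, and the six post-dose values supply that comparison. Objective 3 concerns dose-dependent changes and needs no pre-dose GABA. The method in 5.6.2 is a Pearson correlation of GABA/Cr ratios with the MEG measures, with no mention of GABA change from baseline.
- **That GABA would be measured 0–30 min after dosing under 5.2.1.** The tables do not say which block holds the MRS.
- **That the drug effect would be pulled toward zero.** This could only be inferred from the plasma Tmax of about 60 min in 1.3.1.2, which comes from 5 mg single doses in fasting healthy adults. The documents give no time course for MRS GABA.
- **That 5.2.1 rules out a repeat MEG at 60 min.** With a 30-min break it gives exactly 60. The table allows later times; it does not require them.
- **That MRI timing drifts from visit to visit within 5.2.1.** The MRI and dosing order is identical at each visit, and the variable break comes after both MRI blocks.

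**Conclusion.** The point holds in a limited form. The change-from-baseline GABA endpoint in 5.5, and its analysis in 5.6 and the synopsis, cannot be computed under the synopsis, 3.1.3 and 4.3: 12 values are needed per subject, and 6 are collected, none before dosing. Separately, 5.2.1 gives an incompatible MRI position, with post-dose MRI windows at least about 50–60 min apart, and allows the repeat MEG at about 60–90 min against the stated 60.

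The conclusion rests on reading baseline as pre-dose, as the plan does for MEG, and on the absence of any specified pre-dose or screening MRS. Objective 2 is unaffected once the endpoint is worded to match it. The stated MEG power figures and the sample size do not depend on this point, and the plan gives no power figure for GABA. The endpoint as written should be corrected before any GABA analysis.

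**What to change.** 1. In 5.5, 5.6 and the synopsis, define the GABA endpoint as post-dose GABA at the 15 mg visit and at the 30 mg visit, each minus post-dose GABA at the placebo visit, within subject and reported by dose. This is what Objective 2 already asks.
2. For Objective 3, correlate placebo-subtracted GABA with placebo-subtracted MEG change, one value per subject at each dose, and say so in 5.6.2.
3. If the sponsor does intend change from baseline, state a pre-dose MRS explicitly in 3.1.3, 4.3, 5.2.1 and Table 1. That adds 6 values per subject and about 20 min per visit, or 40 min if the MEGAPRESS time is per hemisphere.
4. Reconcile 5.2.1 with the synopsis, 3.1.3 and 4.3, so that MRS and the post-dose MEG each have one stated time relative to dosing, the same at all three visits. Which flow is intended is for the sponsor to state.

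Items 1, 2 and 4 cost wording and one corrected set of timing tables, with no added scan. A difference between visits may carry visit-to-visit variation that a within-visit change would partly remove. The documents give no GABA variance, so this cannot be sized.

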5.6 Statistical Methods

Primary statistical analyses assess baseline versus post acute-dose (placebo, STX209 15 and 30 mg) changes for (1) M100 auditory latency, and (2) post-stimulus auditory gamma-band activity. For each dependent measure, ANOVAs with dose as a repeated measure will examine baseline versus post acute-dose changes (analyses showing no significant differences across time in baseline M100 and gamma measures will allow use of a single averaged baseline measure). Contrasts of *a priori* interest assess (1) a baseline versus post-acute dose change in the dependent measures averaging across STX209 15 and 30 mg, as well as (2) a change in dependent measures from baseline versus STX209 15 mg versus STX209 30 mg, with this test demonstrating an effect of dose. Secondary and exploratory analyses examine baseline to post acute-dose response changes in MRS auditory GABA concentration as well as associations between MEG functional measures and MRS GABA concentration.

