Study Objective(s)	
 1. To determine whether STX209 produces a significant change in MEG target parameters compared to baseline as well as compared to placebo treatment. Secondly, to determine if the magnitude of such change is influenced by STX209 dose: 0 mg (placebo) versus 15mg versus 30 mg. 2. To determine whether STX209 leads to a significant change in MRS-obtained auditory cortex GABA levels compared with placebo treatment. Secondly, to determine whether the magnitude of the GABA change is influenced by STX209 dose level. 3. To determine if dose-dependent changes in MEG target parameters are correlated to dose-dependent changes in MRS target parameters in auditory cortex.
Test Article(s) (If Applicable)	STX209 (Arbaclofen), a GABA-B agonist and a matching placebo. The active compound is made available to this project by the Clinical Research Associates, LLC (CRA).

Study Design	A randomized acute dose-response design will be employed with a total study duration of 3 weeks. At each visit, baseline MEG will be obtained followed by acute single-dose drug/placebo administration, followed 60 minutes later by repeat MEG. Each participant will receive a single dose of placebo in random order and a single dose of STX209 from smallest to largest (15mg and 30mg). MRI and MRS will be performed immediately following MEG to provide an anatomic basis for source localization as well as to assess acute effects of STX209 administration on MRS estimates of GABA and glutamate.
Number Of Subjects	This is a single site study. 40 male subjects with ASD will be recruited in order to get 38 evaluable subjects.
Study Duration	Subjects will be examined at three separate sessions, at each session receiving in random order a single-dose of placebo, and from smallest to largest a single-dose of STX209 (15mg and 30mg). Each subject's participation will last approximately 4 weeks although participation could be extended up to six or eight weeks if subjects are unable to come four consecutive weeks in a row. The entire study is expected to last one year.
Study Phases	
Screening	Screening for eligibility, obtaining consent, and cognitive and clinical symptom assessments
MEG Assessments	Over a period of 3 visits (at least 1 week apart), baseline MEG exam and then MEG/MRS assessment of STX209 at 15mg and 30mg doses or a single placebo.

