5.7 Sample Size and Power

Forty individuals with ASD (aged 14 to 18 years) will be recruited. In each individual, baseline and post acute-dose imaging data will be obtained at three doses: (1) placebo, (2) STX209 15 mg, or (3) STX209 30 mg. Imaging measures at these three doses will be obtained at least 1 week apart, with the order of placebo and STX209 pseudo-randomized with the constraint that the STX209 15mg dose will be administered before the STX209 30 mg dose (FDA requirement). Assuming lost data or incomplete data sets from 4 individuals, the following power calculations were performed assuming a final sample of 36. As detailed in Section 1.3, given significant between subject variability in auditory cortex neural circuit pathology and thus potential between subject differences with regard to normalization of brain activity in response to STX209, the below statistical analyses conservatively assume a response to STX209 from approximately 50% of the participants. As detailed below, although the study is sufficiently powered to assess a baseline versus a 'general' post acute-dose change (i.e., averaging 15mg and 30mg), there is insufficient data to determine if the study is powered to observe a difference between STX209 15mg and STX209 30mg acute dose brain responses. As such, present data will provide preliminary data to guide future studies investigating STX209 dose differences.

Regarding the primary aims, assuming baseline to post acute-dose changes in M100 latency of approximately 2.5 ms (5 ms = one-half the ASD and control group differences reported in Roberts et al. (2010) and in the range observed in the single Arbaclofen study patient (2-8ms), but half of 5 ms given acute responses in only 50% of the participants), and assuming a standard deviation of similar size (which may be conservative given initial cross-dose averaging), and assuming a response in only 50% of the population, given a sample of 36 and $p = 0.05$, the power to detect a main effect on M100 latency is equal to 0.80. Assuming baseline to post acute-dose changes in post-stimulus gamma-band activity approximately half that reported in Edgar et al. (2015), the power to detect a main effect on gamma activity is approximately 0.70.

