6.1.4 Treatment Compliance and Adherence

Participants are asked to undergo imaging with *three* different dosages (15mg, 30mg, and placebo). Imaging is obtained weekly. If a subject misses an appointment they will be asked to come the following week. The dosage order for that subject will be maintained. If a subject does not complete the entire study the imaging data that was obtained from that subject will be included in the analyses.

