8 STUDY ADMINISTRATION

8.1 Treatment Assignment Methods

8.1.1 Randomization

Across three visits, participants will be randomly assigned a single dose of placebo and in order of smallest to largest a single dose of STX209 (15mg, 30mg). Upon entry into the study, the study pharmacist will assign each subject to one of the below dosage orders, and at each visit providing the research coordinator with the needed pills for that particular visit.

Imaging Assessment 1 Visit 1	Imaging Assessment 2 Visit 2	Imaging Assessment 3 Visit 3
Placebo	15mg	15mg
15mg	Placebo	30mg
30mg	30mg	Placebo

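### 15 mg always precedes 30 mg, and the plan may swap same-visit baselines for one average after a non-significant test, which exposes the 30-v-15 contrast to visit drift with no visit term to absorb it

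*Combined protocol and SAP*

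**What the plan says.** - **Order.** Section 3.2 lists three orders: placebo-15-30, 15-placebo-30 and 15-30-placebo. Section 5.7 describes a pseudo-random order "with the constraint that the STX209 15mg dose will be administered before the STX209 30 mg dose (FDA requirement". Section 8.1.1 says that "the study pharmacist will assign each subject to one of the below dosage orders", and states no ratio or balancing.
- **Baselines.** The Synopsis (Study Design) provides a pre-dose scan every time: "At each visit, baseline MEG will be obtained followed by acute single-dose drug/placebo administration, followed 60 minutes later by repeat MEG".
- **Model.** Section 5.6: "ANOVAs with dose as a repeated measure will examine baseline versus post acute-dose changes". Section 5.6.2 repeats this for M50, M100, MMF and gamma. Neither names a visit, period or sequence term. The only other factor, in 5.7, is a median-split group.
- **Pooling rule.** Section 5.6, with parallel wording in 5.6.2 and the Synopsis: "analyses showing no significant differences across time in baseline M100 and gamma measures will allow use of a single averaged baseline measure". The test and its threshold are not given.
- **Dose contrast.** The second a priori contrast in 5.6 is "a change in dependent measures from baseline versus STX209 15 mg versus STX209 30 mg, with this test demonstrating an effect of dose".
- **Incomplete subjects.** Section 6.1.4: "If a subject does not complete the entire study the imaging data that was obtained from that subject will be included in the analyses". Section 5.7 reaches its final sample of 36 by "Assuming lost data or incomplete data sets from 4 individuals".

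**The concern.** Because 30 mg follows 15 mg in every subject, anything that changes over visits, such as familiarity with the scanner or tasks, can look like a dose effect. The scan taken before each dose is the design's protection: a shift common to both scans of a visit drops out of the change score. The pooling rule gives that protection up on the strength of a non-significant test in about 36 subjects, and so makes the analysis path depend on the data. After pooling, both doses share one baseline, and 30 minus 15 is simply the later post-dose value minus the earlier one.

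At stake is the contrast that 5.6 reads as showing an effect of dose, and dose dependence is part of the primary objective in 2.1. A second, smaller matter is which subjects are analysed: 5.7 and 6.1.4 do not describe incomplete data in the same way, and no missing-data method is named.

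**Working it through.** The plan gives no figure for visit drift or for a 30-v-15 effect, so there is none to reproduce. The 0.80 power in 5.7 concerns a different contrast and is not used here.

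**1. Visit positions (orders from 3.2)**

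| Order | Placebo | 15 mg | 30 mg | 30 minus 15 | Active mean minus placebo |
|---|---|---|---|---|---|
| P-15-30 | 1 | 2 | 3 | 1 | 2.5 - 1 = 1.5 |
| 15-P-30 | 2 | 1 | 3 | 2 | 2 - 2 = 0 |
| 15-30-P | 3 | 1 | 2 | 1 | 1.5 - 3 = -1.5 |
| Mean, equal use | 2.00 | 1.33 | 2.67 | 1.33 | 0 |

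**2. Bias from a linear drift of d ms per visit**
- Same-visit baseline: the drift enters both scans of a visit and cancels, so the bias is 0.
- Averaged baseline, 30 minus 15: (1 + 2 + 1)/3 × d = 1.33d with equal use. It lies between d and 2d whatever the allocation.
- Averaged baseline, active mean minus placebo: 1.5d × (share in the first order minus share in the third), which is 0 when those shares are equal.

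**3. How often the pre-test lets drift through**

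This is a simulation of the two-step rule. Set-up: 36 subjects, 12 per order, no drug effect; a repeated-measures F test on the three baselines at 0.05 (assumed, as the plan states neither test nor level); then a two-sided 0.05 paired test of 30 v 15, on post values if pooled and on same-visit changes if not. The SD is that of the difference between two scans of one subject. Section 5.7 gives an SD of about 2.5 ms without saying whether it belongs to a change or to a single measurement, so 2.5 is the low end of the range. All drift values are assumptions.

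| SD of differences (ms) | Drift (ms/visit) | Baselines pooled | Type I error, whole procedure | Type I error, same-visit baseline |
|---|---|---|---|---|
| 5 | 0 | 95% | 0.05 | 0.05 |
| 5 | 0.5 | 83% | 0.12 | 0.05 |
| 5 | 1 | 45% | 0.18 | 0.05 |
| 2.5 | 0.5 | 46% | 0.18 | 0.05 |
| 7.1 | 1 | 70% | 0.15 | 0.05 |
| 2.5 | 1 | about 1% | 0.06 | 0.05 |

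In the third and fourth rows, type I error among the trials that pool is about 0.33. The last row shows the limit of the problem: a drift that is large relative to the noise is nearly always detected, so pooling is rare.

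**4. Price of a visit term**

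Least squares with subject, dose and visit, 12 per order, complete data. Variances are in units of the residual variance.

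| Contrast | Without visit | With visit | Change in SE |
|---|---|---|---|
| Active mean v placebo | 0.0417 | 0.0417 | none |
| 30 v 15 | 0.0556 | 0.1000 | √(0.1000/0.0556) = 1.34 |
| Each dose v placebo (SE) | 0.236 | 0.258 | 0.258/0.236, about 10% larger |

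Every contrast remains estimable.

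**5. Incomplete subjects**

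Section 5.7 sets aside 4 of 40 (10%) for lost or incomplete data. Section 6.1.4 keeps whatever imaging a non-completer provided. A classical repeated-measures ANOVA needs every condition from each subject, so it could not honour 6.1.4. In two of the three orders the last visit, and so the one missed by a late dropout, is 30 mg.

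**The case against.** The default analysis is change from the same-visit baseline, and an additive drift cancels there. The pooling clause permits an averaged baseline rather than requiring one. The documents report no visit drift. Section 5.7 says there is too little information to judge power for 15 v 30 mg and treats that comparison as preliminary.

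All of this stands, and it limits the point. A reader might infer that any trend over visits biases the trial's dose results in general. The documents do not support that: the exposure arises through pooling, or if the pre-to-post change itself varies by visit, and under balanced orders linear drift leaves the active mean v placebo unbiased. It would also be tempting to set the 1.33 ms bias from a 1 ms drift against the 2.5 ms effect in 5.7. That effect is the baseline-to-post change averaged over doses; the plan assumes no 30-v-15 difference, so the ratio would mean little.

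A reader might also infer that incomplete subjects are discarded. No section says so, and 6.1.4 says the opposite. The four in 5.7 are a planning allowance, and some may have no usable data at all.

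What the objection does not answer is that the rule makes the baseline depend on a test that often misses modest drift, for a contrast that 5.6 still lists as a priori and reads as showing a dose effect.

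**Conclusion.** The point holds for the 30-v-15 contrast. The dose order confounds it with visit, the model has no visit term, and the pooling rule can remove the one protection the design provides. Under the assumed drifts of 0.5 to 1 ms per visit and SDs of 2.5 to 7.1 ms shown above, type I error runs from about 0.06 to 0.18, against about 0.05 with same-visit baselines. These figures rest on assumed drift, a linear trend, an omnibus pre-test at 0.05 and 12 subjects per order, none of which the plan states. Same-visit baselines would not protect if the pre-to-post change itself shifted from visit to visit; only a visit term addresses that.

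The active mean v placebo comparison is not undermined by linear drift if the orders are balanced. The treatment of incomplete subjects is an ambiguity between 5.7 and 6.1.4 to be reconciled, not a stated exclusion. The change should be made before data are analysed; the design need not be altered.

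**What to change.** 1. Delete the baseline pre-test and pooling rule from 5.6, 5.6.2 and the Synopsis. Always use change from the same-visit baseline.
2. Fit a linear mixed model by REML to all available visits, with dose (0/15/30) and visit (1/2/3) as fixed effects and subject as random. Two hemispheres from one visit share visit-level error, so either average them or add a subject-by-visit random effect.
3. Report both a priori contrasts from this model: mean change from same-visit baseline averaged over 15 and 30 mg (visits weighted equally), and 30 v 15. Report active mean v placebo alongside them.
4. State the allocation ratio across the three orders.
5. Reconcile 5.7 with 6.1.4 by saying how subjects with one or two visits enter the analysis. The mixed model can use them; a classical repeated-measures ANOVA would drop them.

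The cost is wording only: no new data or visits, and no change to the dose order. With 12 per order, the 30-v-15 interval is about 34% wider and the SE of each dose v placebo about 10% larger; active mean v placebo is unchanged. These figures come from the model with subject, dose and visit on complete data, and would shift with unequal allocation or missing visits.

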5.4 Primary Endpoint

The primary endpoints are (1) change from baseline to STX209 administration in left and right superior temporal gyrus auditory M50, M100 and MMF latencies, and (2) change from baseline to STX209 administration in left and right superior temporal gyrus auditory gamma total power and phase-locking measures (examined pre- and post-stimulus).

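### Placebo is in the primary ANOVA, but neither a-priori contrast uses it, so the named tests do not answer the placebo part of objective 1; the dose contrast, as worded, does not isolate a difference between doses.

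*Combined protocol and SAP*

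**What the plan says.** Section 2.1 sets the first aim as "To determine whether STX209 produces a significant change in MEG target parameters compared to baseline as well as compared to placebo treatment", and then asks whether the size of the change depends on dose, with the levels "0mg (placebo) versus 15mg versus 30mg".

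Section 5.6 begins by including placebo: "Primary statistical analyses assess baseline versus post acute-dose (placebo, STX209 15 and 30 mg) changes", with "ANOVAs with dose as a repeated measure will examine baseline versus post acute-dose changes". It then names two contrasts of a-priori interest:

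1. "a baseline versus post-acute dose change in the dependent measures averaging across STX209 15 and 30 mg";
2. "a change in dependent measures from baseline versus STX209 15 mg versus STX209 30 mg, with this test demonstrating an effect of dose".

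The synopsis and section 5.6.2 give the same two contrasts. The first primary endpoint in section 5.4 is "change from baseline to STX209 administration in left and right superior temporal gyrus auditory M50, M100 and MMF latencies"; the second, on gamma measures, has the same form. Neither mentions placebo. The power statement in section 5.7 concerns baseline against the average of 15 and 30 mg. That section also says there are too few data to tell whether a 15-versus-30 mg difference is powered.

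**The concern.** At each visit the MEG battery is run, a tablet combination is given, and the battery is run again 60 minutes later (sections 4.3 and 5.1.6). Habituation, fatigue or drowsiness could move the second recording whatever was swallowed. The placebo visit is there to measure that movement. Contrast 1 does not subtract it, so an inert drug with a retest shift can look active.

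Contrast 2 is said to demonstrate an effect of dose. If baseline is one of its levels, it is a joint test that baseline, 15 mg and 30 mg are all equal. Two doses with identical effects violate that hypothesis as surely as two different ones, so a flat response over 15 and 30 mg could be reported as dose dependence.

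The plan names no placebo contrast and no dose-by-time term, and it does not make the contrasts conditional on the overall ANOVA test. The comparison that answers the placebo half of objective 1 is therefore not the stated decision rule.

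**Working it through.** **Inputs.** From section 5.7: n=36, p=0.05 (taken as two-sided), M100 change 2.5 ms, stated power 0.80. The SD is described only as similar in size to the change, so I use 2.5 and 5 ms for the SD (S) of the change averaged over the two active doses. The retest drift r is not in the documents; I assume 0.5 to 2.5 ms.

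**Stated power.** For a paired t-test the noncentrality is λ = √36 × shift / S, with rejection when |t| > 2.030 (35 df).
- S=2.5: λ = 6 × 2.5/2.5 = 6, power above 0.99.
- S=5: λ = 6 × 2.5/5 = 3, power 0.83.
- Exactly 0.80 needs S of about 5.2 ms.

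The S=5 column is therefore closer to the plan's own figure.

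**What each contrast estimates.** Let δ15 and δ30 be the drug effects and r a pre-to-post drift common to all visits.
- Contrast 1: (δ15 + δ30)/2 + r.
- Contrast 2 as worded tests 0 = δ15 + r = δ30 + r.
- Placebo-adjusted: (δ15 + δ30)/2 + r − r = (δ15 + δ30)/2.

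**Contrast 1, inert drug (δ15 = δ30 = 0).**

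| Drift r | λ, S=2.5 | Rejects | λ, S=5 | Rejects |
|---|---|---|---|---|
| 0 | 0 | 5% | 0 | 5% |
| 0.5 ms | 1.2 | 22% | 0.6 | 9% |
| 1 ms | 2.4 | 65% | 1.2 | 22% |
| 1.25 ms | 3.0 | 83% | 1.5 | 31% |
| 2.5 ms | 6.0 | >99% | 3.0 | 83% |

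**Contrast 2 as worded, δ15 = δ30 = 2.5 ms, r=0** (simulated three-level repeated-measures F test). It rejects in over 99% of trials at S=2.5 and in about 63% to 77% at S=5. The S=5 spread depends on how baseline is handled: 63% with three pooled baselines, about 75% to 77% with a single baseline, and 72% with pooled baselines when every recording is independent with SD 5 ms. The direct 30-versus-15 comparison of changes rejects in about 5%.

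**Placebo-adjusted contrast.** With an inert drug it rejects in about 5% at every drift simulated (0, 1 and 2.5 ms). Its power depends on the correlation ρ between visits' changes, which the documents do not give. The per-visit change has SD s = S/√((1+ρ)/2), and the contrast has SD s√(1.5(1−ρ)). For a 2.5 ms effect and S=5:

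| ρ | SD of contrast | Power, n=36 | n for 80% |
|---|---|---|---|
| 0 | 8.66 ms | 0.39 | 97 |
| 0.25 | 6.71 ms | 0.59 | 59 |
| 0.5 | 5.00 ms | 0.83 | 34 |
| 0.75 | 3.27 ms | 0.99 | 16 |

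At S=2.5 power is at least 0.92 for every ρ from 0 to 0.75.

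**Linear trend over 0, 15 and 30 mg.** The doses are equally spaced, so the weights are −1, 0, +1 and the trend is simply 30 mg minus placebo. Its SD is s√(2(1−ρ)). With δ15 = δ30 = 2.5 ms and S=5, ρ=0 gives SD 10.0, λ = 1.5 and 31% rejection; ρ=0.5 gives SD 5.77, λ = 2.6 and 71%. It does not separate 30 mg from 15 mg either.

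**Visit order.** In all three orders (sections 3.2 and 8.1.1) 15 mg precedes 30 mg. Assume equal numbers per order, which the plan does not state. Code 30 mg as +1, 15 mg as −1 and placebo as 0. Over the three orders the squares sum to 6 and the visit totals are −2, 0 and +2, so visit absorbs (4 + 0 + 4)/3 = 8/3 and leaves 10/3. Adjusting for visit is possible, but it multiplies the variance of 30 minus 15 by 6/(10/3) = 1.8. Placebo occurs once at each visit across the orders, so with equal numbers the placebo-adjusted contrast is already balanced for visit.

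**The case against.** A reader might infer that the trial tests its main claims without placebo. The documents do not support that. Section 5.6 puts placebo among the conditions of the primary analysis and makes dose the repeated factor. A dose test on change scores over placebo, 15 and 30 mg cancels a common drift, and in simulation it stayed at about 5%. What stands is narrower: the plan never says that this term is the one that decides, and the contrasts it does single out are unprotected.

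A reader might also take contrast 2 as certainly mixing baseline into the dose test. Its wording can be read as comparing changes from baseline between the two doses, which would remove the equal-doses problem. Section 5.7 also treats the 15-versus-30 mg difference as preliminary, and the synopsis labels the study exploratory for MEG. The ambiguity is real, but baseline is listed as a level, and placebo is absent on either reading.

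The size of the problem rests on a drift that nobody has measured in these documents. At SD 5 ms and 0.5 ms drift, contrast 1 rejects in only 9%. The 83% at 1.25 ms needs SD 2.5 ms, which does not fit the stated power.

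Finally, objective 1 does ask for change against baseline, so contrast 1 answers part of it and should not be dropped.

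**Conclusion.** The concern holds in this form: the two named contrasts do not answer the placebo part of objective 1, and no placebo comparison is named as the decision rule. This follows from the text alone.

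How often contrast 1 would mislead depends on the assumed drift and SD. At about 5 ms, the SD closest to the plan's power figure, an inert drug would be called active in 9% of trials at 0.5 ms drift, rising to 83% at 2.5 ms, against a nominal 5%. The contrast 2 result holds only on the literal reading; on the other reading only the missing placebo remains. Failure to reproduce 0.80 exactly is a separate matter and does not affect this conclusion.

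**What to change.** In the synopsis and sections 5.6 and 5.6.2:

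- Define the drug-effect contrast as the mean of the 15 and 30 mg changes, each post-dose minus same-day baseline, minus the change at the placebo visit. Name it as the test that decides whether STX209 has an effect.
- Keep the pre-post contrast on active drug, because objective 1 asks for it, but label it supportive and not evidence of a drug effect on its own.
- Replace contrast 2 with the 30 mg minus 15 mg difference in change, with visit in the model, labelled exploratory in line with section 5.7.
- If a comparison over 0, 15 and 30 mg is also reported, describe it as a test of any difference from placebo. Do not present a linear trend as showing that 30 mg differs from 15 mg.
- Align section 5.4 with the placebo-adjusted contrast, and restate power in section 5.7 for it, giving the assumed SD and between-visit correlation.

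No new data are needed, since every subject is already scheduled for a placebo visit. The cost is power: at SD 5 ms and low between-visit correlation, 36 subjects fall well short of 0.80, and the plan should say so. The visit-adjusted dose comparison is also less precise than an unadjusted one.
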